3.0 Objectives

Specific Aims

Aim 1. Characterize the GATs received by trans Vets in VA and/or CC. We will expand our VA cohort of 9,608 trans Vets² (IIR 17-238) from 2006-18 to the most recent year of data available at the time of funding. We will then add CC data to characterize the GATs received by trans Vets in VA only, CC only, and VA and/or CC. We will also expand our ongoing work on receipt of hormone therapy in VA to examine it in CC as well.

Aim 2. Identify barriers and facilitators associated with receipt of desired GATs in VA and CC. We will survey a national sample of trans Vets with new gender dysphoria diagnoses identified from Aim 1. Among trans Vets who desire GATs, we will determine SDOH barriers, other barriers, and facilitators associated with receipt of desired GATs in VA and/or CC. Among trans Vets who did not desire GATs, we will determine reasons for not wanting GATs to

distinguish between trans Vets who truly do not desire GAT (e.g., due to nonbinary identity) and trans Vets who may desire GATs if certain barriers to GAT access could be addressed.

^{5.0} **Aim 3. Understand trans Vet experiences related to GAT access in VA and CC.** From Aim 2, we will recruit a purposive sample of trans Vets who received all desired GAT(s), some desired GAT(s), and no desired GAT(s). We will also recruit a national sample of LGBTQ+ Veteran Care Coordinators, who are point persons for trans Vets at VA sites.²⁷ Participant interviews will explore experiences and perspectives on GAT access in VA and CC, how SDOH and other barriers influence GAT access and desire, and suggestions for improving GAT access.

Relevance

Informed by study findings and in partnership with our Stakeholder Advisory Group, we will develop patient-centered implementation strategies to improve GAT access. We will deploy these strategies in a follow-up hybrid implementation effectiveness study to mitigate barriers and enhance facilitators to improve GAT access in VA and CC and promote trans health equity. This work addresses HSR&D priorities of health equity/SDOH, access to care, MISSION Act, underserved LGBTQ+ Veterans; and is informed by our ongoing IIR 17-238.

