5.0 Study Procedures

5.1 Study Design

This is an observational multi-method cross-sectional study with transgender Veterans that will identify barriers and facilitators associated with GAT receipt among trans Vets who desire GATs. We will also identify patient-centered strategies to address barriers and enhance facilitators to improve GAT access. The proposed study will use a mixed-methods design, with three aims. We begin with obtaining national VA data to provide a foundational lay of the land on the GATs received by trans Vets in VA and/or CC (database Aim 1). Next, using a national cross-sectional survey, we will identify barriers and facilitators associated with receipt of desired GATs in VA and CC (survey Aim 2). Finally, by interviewing trans Vets and LGBTQ+ VCCs, we

will understand experiences and perspectives on GAT access in VA and CC, and how to improve this access in VA and CC (qualitative Aim 3).

Database Aim 1: We will expand our VA cohort of 9,608 trans Vets (IIR 17-238) from 2006-18 to the data available at the time of funding. We will add CC data to determine the types of GATs received by trans Vets in VA and/or CC. Aim 1 of the study will consist of all Veterans with documentation of a gender dysphoria (GD) diagnosis code in the VA or in CC from 1999 to the current year for which VA and CC data is available.

Survey Aim 2: We will survey a national sample of up to 1,500 trans Vets with a documentation of a gender dysphoria (GD) diagnoses identified from Aim 1 in the VA or CC in the past 2 years at the time of funding. Among trans Vets who desire GATs, we will determine barriers, and facilitators associated with desired GAT receipt. Among trans Vets who did not desire GATs, we will determine reasons for not wanting GATs. Veterans will be invited by postal mail, email, and phone to participate in a single survey. Similar to our pilot testing recruitment, we will also advertise the survey on VA's LGBTQ+ Health Office website and we will work on recruitment with LGBTQ+ Veteran Care Coordinators (VCCs). Veterans will be encouraged to complete the survey online but will have the option to complete the survey by phone or mail if desired. Data from the survey will be linked to CDW data (available through VINCI) via a study ID, and the crosswalk file will be stored in a separate secure file and will only be accessible to study team members.

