Qualitative Aim 3: From Aim 2 participants, we will recruit a purposive sample of approximately 70 trans Vets. We will also recruit a national sample of approximately 20 LGBTQ+ Veteran Care Coordinators (VCCs). We will seek to understand experiences and perspectives on GAT access in VA and CC, how barriers, and facilitators influence GAT access and desire, and how to improve GAT access in VA and CC.

Risks and Benefits

Anticipated risks and protection against anticipated risks

Database Aim 1

This aim involves retrospective secondary data analyses of existing data. The principal risk to human subjects from these aims is loss of confidentiality, which will be minimized.

We will take several steps to protect participants against potential risks inherent to the proposed research in this aim. The study team has extensive experience conducting secondary data analyses that require strict data security. The Bedford VAMC healthcare systems and VINCI also have well-developed systems and training for preserving data security and confidentiality. These systems will be augmented by the additional security provided by the VINCI system. Data for all participants will be kept strictly confidential by the following means: Source data files will be stored behind the VA firewalls. These data files will be accessed only by data analysts and investigators working on this study. All investigators and project staff will have received IRB and HIPAA training prior to participation in this study. Individual patient identifier information will be removed from study data files as soon as possible after database linkage. In order to avoid any negative consequences of loss of confidentiality, clinicians and other related staff will not be privy to the individual findings, as data will be presented in aggregate in publications and presentations. Unique study-specific identifiers will be assigned to support accurate linkage of data on the same individuals across multiple data files. We will maintain an encrypted secure data dictionary linking the study identifier to the personal identifiers, which will be kept in compliance with the VA Records

Control Schedule after the IRB approval. Analysis files of de-identified data will be created by standard SAS and related analytic programs.

Survey Aim 2

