and all information and data security protections are followed. The funds for the gift cards have been approved in the study budget by VA HSR&D, which is funding the study. If the participant does not complete the survey, we will use the information/incomplete data the participant already provided in the survey, unless they notify us that they do not want their information to be used.

Qualitative Aim 3:

Transgender Veterans: We anticipate interviewing ~ 70 trans Vets. We will seek diversity in the sample based on race, gender identity, VA region to ensure geographic representation and care received in VA vs. CC.

We will recruit qualitative interview participants from survey respondents. We will ask survey respondents in the survey if they would be willing to participate in a follow-up telephone interview. The following survey question will be reviewed for interest: "Our research team plans to interview trans Vets to learn more about their experiences accessing gender-affirming treatment in VA and VA Community Care. Would you be interested in participating?"

VA staff will mail or email potential participants a letter and an Information Statement alerting them about the interview opportunity, providing details about the individuals' right as a research participant. The letter will explain that the survey is entirely voluntary and that if they choose not to participate or to end the interview prior to completion, there will be no penalties or loss of VA benefits. The letter will make clear that the interview responses provided are confidential and that the Veteran's name will not be used in any report of the results. The IRB's telephone number will be provided as a means for the potential participant to use to verify that the study constitutes VA research. Additionally, the telephone number of the study project coordinator will be provided for the Veteran to call with questions about the study or if they wish to opt out of the study.

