5.5 Study Evaluations

Database Aim 1. Data obtained from the VA administrative data will include identifiers (e.g., name, postal address, email address, phone number), demographics (e.g., age, sex, region, marital status, enrollment priority), vitals (e.g., weight and height), and some behaviors (e.g., smoking and alcohol misuse data) from health factors data. Participants' medical history, diagnoses, treatments, and health care utilization will also be ascertained for both VA and CC from VA administrative data.

Survey Aim 2. Measures will include demographics, setting of gender-affirming treatment receipt (VA, CC), adverse social determinants of health (e.g., housing instability, unemployment), receipt of gender-affirming treatments (e.g. hormones, psychotherapy), barriers and facilitators to gender-affirming treatment in VA and CC, satisfaction with gender-affirming treatment, desire for gender-affirming treatment, depression, anxiety, suicide, minority stress, health conditions/comorbidities, barriers to VA care, quality of life, and smoking. For the pilot testing of the survey, we will elicit open-ended and close-ended feedback about the survey from Veterans to allow for refinement of the survey prior to national deployment of the survey.

Qualitative Interview. Data will be collected from trans Vet participants and LGBTQ+ VCCs during a 45-60-minute and a 30-45 minute telephone/Microsoft teams-based semi-structured interview. Interview guides will contain open-ended questions and areas to query. We will explore trans Vet experiences with barriers and facilitators impacting their ability and desire to access gender-affirming treatments in VA and CC. We will also query them on whether they have used any services and resources in VA and in the community to mitigate these barriers and suggestions on how gender-affirming treatment access might be improved in VA and CC. In addition, we will ask trans Vets about their awareness of gender-affirming treatment availability and coverage in the VA and differences in experiences in accessing gender-affirming treatments in VA and CC.

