5.6 Data Analysis

Database aim 1: The data analyst under the supervision of the PI will produce summary statistics (e.g., proportions, means) for gender-affirming receipt in VA and/or CC (VA/CC). We will characterize gender-affirming receipt by: 1) patient characteristics, including demographics (e.g. race), comorbidities (e.g. mental health conditions) commonly reported by trans individuals, utilization of VA care (e.g. primary care), 2) site (e.g. region, rural/urban) and 3) setting (VA/CC). As appropriate, two-sided chi-square test (categorical variables), t-test (continuous variables) or their nonparametric equivalent tests will be used to test for the statistical significance of the associations of these patient and site characteristics with gender-affirming receipt. We will also compare the characteristics of patients receiving gender-affirming treatment through VA vs. CC.

Survey aim 2: Our analytical goal is to identify barriers and facilitators associated with receipt of desired gender-affirming treatments in VA and/or CC. In keeping with this goal, the data analyst under the supervision of the PI, will conduct the following analyses:

Descriptive analyses: We will obtain summary statistics (e.g., proportions, 95% confidence intervals, etc.) of the distribution of each gender-affirming treatment, degree of receipt of desired gender-affirming treatments, barriers, and facilitators of gender-affirming treatment. We will characterize the degree of receipt of desired gender-affirming treatments in VA and/or CC. We will also characterize barriers and facilitators by degree of receipt of desired gender-affirming treatments in VA and/or CC, recognizing that trans Vets who received all desired gender-affirming treatments could encounter barriers in receipt of these gender-affirming treatments and trans Vets who received no desired gender-affirming treatments could encounter facilitators in trying to receive gender-affirming treatments. We will also characterize the degree of receipt of desired gender-affirming treatments, barriers and facilitators by age, race/ethnicity, gender identity (transfeminine, transmasculine, non-binary), and region.

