Primary analyses: We will conduct bivariate analysis to assess the unadjusted relation of barriers and facilitators with the dependent variables, receipt and desire of gender-affirming treatments in VA and CC. As appropriate, two-sided chi-square tests (categorical variables) or their equivalent non-parametric tests will be used to test the significance of any group differences. We will obtain odds ratios (ORs) and 95% confidence intervals (CI) from separate multivariable logistic regression models, to assess associations between barriers and facilitators for the dependent variables. A multinomial logistic regression model will be used to evaluate associations of barriers and facilitators with the ordinal dependent variable: degree of receipt of desired gender-affirming treatments. These models will adjust for covariates, such as age, race/ethnicity and gender identity. Further, depending on the distribution of respondents across sites, we will examine the distributions of the independent and dependent variables as well as the respondents' characteristics across sites. If there is substantial variation across sites and there are adequate number of respondents (at least 5) in each site, we will adjust for clustering of respondents within sites in the analyses. We will combine sites with small sample sizes into a single cluster for the analyses.

Secondary analyses: To assess interrelationships between barriers, we will examine the overlap of barriers by ascertaining the proportion of trans Vets with various combinations of barriers. To examine this overlap, we will create two variables: 1) a categorical variable, indicating combinations of different barriers (e.g., housing instability only, housing instability and employment, housing instability, unemployment and need to travel for gender-affirming treatments, etc.); 2) number of barriers. We will also explore the effects of these variables in models described in the primary analyses.

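### Aim 3 asks how barriers influence desire for gender-affirming treatments (GATs), but every named interview stratum presupposes desire, so Veterans who report none have no planned interviews

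*Combined protocol and SAP*

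**What the plan says.** Section 3.0 sets the Aim 3 strata: "From Aim 2, we will recruit a purposive sample of trans Vets who received all desired GAT(s), some desired GAT(s), and no desired GAT(s"). The Abstract gives the same three groups under Research Design. No other section names a stratum.

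Desire is a stated topic of the same aim. Section 3.0 says that the interviews will explore "how SDOH and other barriers influence GAT access and desire". Section 5.1 repeats this: "how barriers, and facilitators influence GAT access and desire, and how to improve GAT access in VA and CC". Section 5.5 puts it into the interview content: "We will explore trans Vet experiences with barriers and facilitators impacting their ability and desire to access gender-affirming treatments in VA and CC". Section 5.6 plans case studies covering both desire and receipt.

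Section 5.2 sets the target of about 70 Veterans and seeks diversity on "race, gender identity, VA region to ensure geographic representation and care received in VA vs. CC".

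For the survey (Aim 2), section 5.1 says: "Among trans Vets who did not desire GATs, we will determine reasons for not wanting GATs". Section 3.0 gives the purpose, which is to separate Veterans who truly do not want treatment from those who might want it if an obstacle were removed. In section 5.6 the primary analyses relate "barriers and facilitators with the dependent variables, receipt and desire of gender-affirming treatments in VA and CC".

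**The concern.** To learn how a barrier weakens or removes desire, the most direct informants are people whose desire it may have removed. Section 3.0 recognises that such Veterans may exist and uses the survey to find them. The interview plan then gives them no place.

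This matters because the Abstract describes a sequential explanatory design, in which interviews follow the survey in order to explain it. The survey will produce a list of reasons for not wanting treatment. Under the named strata, no interviews are planned with the people who gave those reasons. The implementation strategies are to draw on the combined interview and survey findings (section 5.6). For this group they would rest on the survey answers, with first-hand interview accounts only by chance.

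**Working it through.** The documents give no sample size or precision figure for desire, so the check is mainly a comparison of sections.

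**1. Does any named stratum include Veterans without desire?** The strata are all, some, or none of the desired treatments received. The third could be misread as having no desire. Section 5.6 rules that out, because it describes the group as people making an attempt: "trans Vets who received no desired gender-affirming treatments could encounter facilitators in trying to receive gender-affirming treatments". All three strata consist of Veterans who want treatment.

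**2. Does another section add the missing group?**
- Section 5.1 (Qualitative Aim 3) and section 5.4 mention only a purposive sample of about 70.
- Section 5.2 lists race, gender identity, region and VA versus Community Care. Desire status is not listed.
- Section 5.2 recruits from survey respondents who say they are interested, using a question about experiences of accessing treatment. A Veteran who never sought treatment may not see that as addressed to them.
- The fallback in section 5.2 has coordinators give a letter to all transgender Veterans at their sites. It applies only if recruitment proves difficult, and it sets no cell.

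**3. Can other interviewees fill the gap?** About 20 care coordinators will be interviewed, but their accounts are second-hand, and section 5.5 describes their content in terms of access rather than desire. A Veteran who wants hormones but has given up on surgery fits a named stratum and can describe lost desire for one treatment. That covers part of the question, but not Veterans who want nothing.

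**4. Size.** Interviews reserved for Veterans without desire: 0 of about 70.

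**5. What would a fourth stratum cost?** The documents give no split across strata, so equal allocation is assumed.
- Now: 70 / 3 = 23.3 per stratum.
- With 10 moved: (70 − 10) / 3 = 20.0 per stratum.
- With 15 moved: (70 − 15) / 3 = 18.3 per stratum.

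The loss is about 3 to 5 interviews per existing stratum.

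**6. Are there enough respondents to draw from?** The share reporting no desire is not given. Assume 5% to 20% of the 1,500 maximum: 0.05 × 1,500 = 75, and 0.20 × 1,500 = 300. Fifteen interviews would need 15 / 75 = 20% of that group at the low end, or 15 / 300 = 5% at the high end. Ten would need 13% or 3%. A smaller survey yield shrinks the pool in proportion, and the number citing a barrier is unknown.

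**7. Aim 2.** Modelling desire on barriers needs comparable barrier items from Veterans with and without desire. Section 5.5 lists SDOH, barriers, facilitators and desire as survey measures without restricting any of them to one group. Section 5.1 (Participant burden) and section 5.6 (Missing data) mention branching logic but do not say what is branched. The population for the desire models is not named.

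**The case against.** The strongest reply on Aim 3 is that directed content analysis and case studies need no comparison group, that desire is specific to each treatment, and that section 5.4 excludes nobody. All of this is correct. It means that some evidence on desire will emerge, and that a Veteran without desire could be interviewed by chance. It would be too strong to say that the interviews cannot show any effect of barriers on desire. The reply does not answer the sampling point: a purposive sample is built from the cells it names, and this cell is missing although the protocol singles the group out.

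A reader might also infer that the survey has no comparison group for desire: that barrier items go only to Veterans who want treatment, so the desire models cannot be estimated. The documents do not support this. The restriction to Veterans who desire GATs in sections 3.0 and 5.1 defines who is analysed for receipt of desired treatments, an outcome with no meaning for someone who desires none. It does not describe survey routing. Section 5.4 excludes no one on desire, section 5.5 lists the measures without limit, and section 5.6 presupposes barrier data in both groups. Survey data are also to be linked to VA records (section 5.1), and the team's earlier work with VA data covered housing instability, financial strain and violence (section 2.0). Some barrier information could therefore exist whatever the routing.

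A further fair point is that some barriers, such as delay in receiving treatment, may not be answerable by someone who never sought it. An identical block for everyone is not the right request.

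**Conclusion.** The point holds for Aim 3. Influence on desire is a repeated interview goal, all three named strata presuppose desire, and no interview out of about 70 is reserved for Veterans who report none. The objective is weakened rather than defeated, because partial desirers and coordinators can contribute something. The conclusion rests on reading the named strata as the sampling frame for the purposive sample, which the Abstract and section 3.0 support and no other section contradicts.

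For Aim 2 only a request for clarification remains. Veterans without desire are in the survey, and nothing shows that barrier items are withheld from them. What is missing is a statement of who answers those items and which population the desire models use. The access and receipt objectives are unaffected. This is an inexpensive improvement, not a fault that undermines the study.

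**What to change.** 1. Within the planned 70 or so interviews, add a fourth stratum of survey respondents who report no desire for GATs, giving priority to those whose stated reason is a barrier. Ten to 15 interviews is a workable example. Check that the wording of the interview-interest question also fits Veterans who have not sought treatment. The cost is about 3 to 5 fewer interviews in each existing stratum under equal allocation, with no increase in the total. If the stratum is not added, narrow the Aim 3 desire objective to Veterans who want at least one treatment.

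2. For Aim 2, confirm in section 5.5 that the SDOH, barrier and facilitator items that apply whether or not a Veteran has sought treatment are asked of all respondents before any branch on desire. Name the analysis population for the desire models in section 5.6. If this is already the design, the cost is two sentences. If not, the survey becomes somewhat longer for respondents without desire.
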